6.2.2 Assay Methodology

Pharmacokinetic samples will be analysed for the concentration of PP-001 using a validated liquid chromatography-tandem mass spectrometry method at the bioanalytical laboratory.

6.3 Pharmacodynamic Procedures

Detailed ophthalmic examination will be used to evaluate the pharmacodynamic effects of PP-001 on the eye. All procedures should be performed at the times outlined in the Time and Events table (Table 1 and Table 2) and will be performed on both eyes in order to provide a non-treated comparison. Further details on the conduct of the ophthalmic examinations can be found in the SRM.

6.3.1 Best Corrected Visual Acuity

Best corrected visual acuity will be measured in both eyes using an Early Treatment Diabetic Retinopathy Study (ETDRS) chart. Subjects will be asked to read the smallest letters they can from a chart.

6.3.2 Visual Field Measurement

A 30° visual field measurement will be conducted using computerised perimetry. Subjects will be asked to identify when they can see flashing lights at the periphery of their vision whilst staring straight ahead. The lights will gradually move towards the centre of the screen, so identifying the extent of the subject's peripheral vision.

6.3.3 Intraocular Pressure

Intraocular pressure will be measured using Goldmann contact tonometry. This involves pressing the tonometer prism against the cornea after topical anaesthesia in order to determine the intraocular pressure.

6.3.4 Slit Lamp Examination

A slit lamp will be used to examine the conjunctiva, cornea and anterior chamber including grading of cells and haze (classified according to Standardization of Uveitis Nomenclature Working Group criteria), lens (classified according to Lens opacities classification system II) and vitreal haze (classified according to Standardization of Uveitis Nomenclature Working Group). Conjunctival hyperemia will be scored using a standardized photographic scale derived from McMonnies

grading (0-5) (McMonnies & Chapman-Davies 1987) in cohorts 1-3. In cohort 4, conjunctival hyperemia will be scored according to the scale proposed by Efron et al. 1998, see chapter 6.3.9.

6.3.5 Dilated Fundoscopy

Examination of the fundus (retina) will be carried out as part of the eye exam following dilation of the subject's pupils. Slit lamp biomicroscopy of the fundus will be performed as part of this procedure.

6.3.6 Fundus Photography

While the subject's pupils are dilated the eye, retina, retinal vasculature, optic disc, macula and posterior pole will be photographed using a retinal camera. Vitreous haze will also be documented if present.

6.3.7 Amsler Grid

To test for macular degeneration, subjects will be asked to wear their normal glasses (if applicable) and to look at an Amsler grid. With one eye covered, subjects will be asked to state if any of the lines appear wavy, blurred or distorted, and whether there are missing or dark areas in the grid. The test will be repeated for both eyes.

6.3.8 Ocular surface disease index (OSDI)

Symptoms of dry eye will be assessed using the Ocular Surface Disease Index (OSDI). The questionnaire that underlies the OSDI is specifically designed for patients with ocular surface disease and asks patients about the frequency of specific symptoms and their impact on vision-related functioning.

6.3.9 Assessment of conjunctival hyperemia

Conjunctival hyperemia will be assessed by the investigator during slit lamp examination according to the scale proposed by Efron et al. 1998:

- (0) = None
- (1) = Trace
- (2) = Mild
- (3) = Moderate
- (4) = Severe

6.3.10 Tear film osmolarity

Tear film osmolarity will be measured non-invasive with a commercially available instrument (TearLab®, OcuSens Inc, San Diego, USA). The TearLab® technology uses an approach that concentrates laboratory functions on a single chip that requires less than 50 nL of tear fluid in order

to measure tear osmolarity. The system uses a handheld pen on which the ophthalmologist places the noninvasive laboratory chip test card. Then the tear sample is collected by pressing the tip of the pen towards the conjunctiva adjacent to the lower lid margin. The collection of the tear sample takes usually less than 30 seconds and is painless for the subject.

6.3.11 Corneal fluorescein staining

Minims-Fluorescein Sodium 2.0% eye drops will be used to detect corneal epithelial defects. As grading scale for corneal damage, the NEI/Industry Workshop guidelines will be used (Lemp 1995). The cornea will be divided into five sectors (central, superior, inferior, nasal and temporal), each of which is scored on a scale of 0–3, whereas 0 means no staining and 3 means maximum staining, with a maximal score of 15.

6.3.12 Tear film break up time (BUT)

Tear break up time will be measured following the guidelines published in the Report of the International Dry Eye Work Shop (DEWS) 2007. Briefly, Minims-Fluorescein Sodium 2.0% eye drops are applied in the conjunctival sac of the eye. The patient is instructed to blink naturally without squeezing several times to distribute the fluorescein. Within 10 - 30 seconds after fluorescein instillation, the patient is asked to stare straight ahead without blinking, until told otherwise. By the means of a stopwatch the time between last complete blink and first appearance of a dry spot is recorded. Once breakup of the tear film is observed, the patient will be instructed to blink freely.

6.3.13 Conjunctival staining using lissamine green

Lissamine green (LG, EasyOpht, Italy) will be used to detect conjunctival defects. Before placing the strip in the lower fornix of the eye, a drop of sterile saline must be added to the strip. As grading scale for conjunctival damage, the NEI/Industry Workshop guidelines will be used (Lemp 1995). Both nasally and temporally, the conjunctiva is divided into a superior paralimbal area, an inferior paralimbal area and a peripheral area with a grading scale of 0–3, whereas 0 means no staining and 3 means maximum staining, with a maximal score of 9 for the nasal and temporal conjunctiva.

6.4 Prior and Concomitant Medications

Regular use of any ocular agents within 60 days prior to Day 0 will be assessed. Prior and concomitant medications that will be recorded include prescription medications, dietary supplements/vitamins and over-the-counter medications. Topical medications will be recorded only if used as a treatment for an AE. The minimum requirement is that drug name, indication and the stop and start dates of administration are to be recorded.

6.4.1 Prior Medications

A medication history will be taken at Screening. Regular use of any ocular agents within 60 days prior to Day 0 will be assessed. All non-ocular medications taken within 1 week before Day 0 will be entered into the eCRF.

6.4.2 Concomitant Medication

All concomitant medications taken during the study will be recorded in the subject's eCRF. All concomitant medications taken during the outpatient phase will be recorded by the subject in a diary card and transcribed by site staff into the eCRF.

In cohort 4, subjects will be handed out a bottle of topical lubricants (Genteal HA, Laboratoires Thea, France) as standard of care treatment for the control eye as needed. Subjects will be instructed to document instillation dates and times for Genteal HA eye drops in a diary card and entries will be transcribed by site staff into the eCRF.

6.5 Prohibited Medications

The following medications are prohibited during this study and for at least five half-lives prior to Day 0:

- Local or systemic biologicals (i.e., tumour necrosis factor-blockers, B cell-blockers, cytokines, cytokine-blockers, receptor antagonists)
- Cyclophosphamide or chlorambucil
- Immunosuppressive, immunomodulatory or steroid treatment
- Any anticoagulant or thrombocyte aggregation inhibiting agent (marcumar, warfarin, heparin, enoxaparin, apixaban, rivaroxaban, pentosanpolysulfate, dabigatran, aspirin and others)
- Any systemic antibiotic treatment

6.6 Non-Pharmacologic Treatments and Procedures

Non-pharmacologic treatments and procedures (e.g., diagnostic) that occur during the study will be entered into the eCRF, including the date and reason for the treatment/procedure.

6.7 Total Blood Volume Collected

Subjects in cohorts 1-3 will have approx. 50 mL of blood collected for safety and pharmacokinetic evaluations during the study. Subjects in cohort 4 will have approx. 46 ml of blood collected for safety evaluations during the study.

6.8 Discontinuation from Treatment or Study

Subjects are free to withdraw from the study at any time for any reason. Subjects may be withdrawn from the study at the discretion of the Investigator. Once a subject has been withdrawn from the study, they may not be re-entered. Subjects who withdraw or who are withdrawn from the study before day 21 will be replaced. Subjects who are withdrawn due to AEs will not be replaced. If a subject is discontinued from treatment or from the study, the reason for discontinuation will be collected in the eCRF.

If a subject is prematurely withdrawn from study treatment, the Investigator should make every effort to retain the subject in the study and perform all procedures scheduled for the follow-up. Any subject withdrawn from treatment due to an AE, SAE or clinically significant safety value will be evaluated by the Investigator, or a monitoring physician, and will be treated and/or followed up until the symptoms or values have either resolved or are assessed as stable by the Investigator.

6.8.1 Discontinuation from Study

A subject may be discontinued prematurely from the study for the following reasons:

- Withdrawal of consent by subject (if provided, the reason should be specified in the eCRF)
- Lost to follow-up
- Death
- Physician decision (i.e., assessment that it is not in the subject's best interest to continue, or another reason; the reason should be specified in the eCRF)
- The Sponsor may terminate the study at any time

6.8.2 Individual Stopping Criteria

If an individual subject meets one or more of the following criteria the DSMB and Investigator will discuss whether the subject should be withdrawn from the study or whether dosing should be postponed until the criterion is no longer met:

- Subject develops a concurrent illness, condition or procedural complication that would interfere with the subject's continued participation
- Subject experiences a study drug-related SAE as determined by the Investigator

Subjects may also be withdrawn from the study at any time at the discretion of the Investigator for other safety or tolerability reasons or for behavioural or administrative reasons.

A subject may also withdraw from the study at any time at their own request.

If a subject is prematurely withdrawn from study treatment, the Investigator should make every effort to retain the subject in the study and to perform all procedures scheduled for the follow-up visit. Any subject withdrawn from treatment due to an AE, SAE or clinically significant abnormal laboratory test value will be evaluated by the Investigator, or a monitoring physician, and will be treated and/or followed up until the symptoms or values have either resolved or are assessed as stable by the Investigator.

6.8.3 Study Stopping Criteria

Dosing of further subjects will be halted if the following criterion is met:

- Severe AEs classified as being possibly, probably or definitely study-drug related or potential major safety concerns as identified by the Investigator after consultation with the DSMB are reported in more than 50% of subjects in the same cohort

Dosing will be stopped or the dose decreased if:

- One subject on any dosing day shows a possibly, probably or definitely study-drug-related SAE judged by the Investigator after consultation with the DSMB, or other potential major safety concerns are identified by the Investigator in agreement with the DSMB

6.8.4 Lost to Follow-up

If a subject does not report to the study site for a scheduled visit, study personnel will make four contact attempts: three attempts will be made to contact the subject by telephone; if these are unsuccessful then a letter will be sent by registered/signed for delivery. The subject will be considered lost to follow-up if (1) upon receipt of delivery confirmation of the letter the subject does not contact the site or (2) the letter is returned as undeliverable within 7 days.

6.9 Premature Termination of the Trial

In the event of any SAE, which, in the Investigator's opinion, justifies termination of the trial, dosing will be stopped and the Sponsor will be informed immediately. The Sponsor and Investigator reserve the right to terminate this trial should serious or severe AEs or any other safety issue occur during the trial. If the trial is terminated prematurely, the Investigator will return all eCRFs to the Sponsor, and the Sponsor or Investigator, as appropriate, will document the reasons for termination. The Sponsor will ensure that the relevant regulatory agencies and main research ethics committees are notified

6.10 Contraceptive measures

Women of childbearing potential and fertile men need to adhere to contraceptive measures in accordance with the "Recommendations related to contraception and pregnancy testing in clinical trials, September 2014" of the Clinical Trials Facilitation Group.

Male and female subjects must ensure that one highly effective method of contraception combined with an acceptable method of contraception is used for the entire duration of the study, from first dose up to the study follow-up visit, and must refrain from becoming pregnant or fathering a child in the 3 months following the last study drug administration. Male subjects must agree with their female partners prior to screening to use the above specified methods of contraception while receiving protocol-specified medication, and for 3 months after stopping the medication.

- Highly effective methods of birth control are defined as those that result in a low failure (i.e., < 1 % per year) when used consistently and correctly, such as:
 - combined (oestrogen and progestogen containing) hormonal contraception associated with inhibition of ovulation (oral, intravaginal, transdermal)
 - progestogen-only hormonal contraception associated with inhibition of ovulation (oral, injectable, implantable)
 - intrauterine device
 - intrauterine hormone-releasing system
 - bilateral tubal occlusion

- vasectomised partner
- sexual abstinence
- Acceptable birth control methods are defined as those that result in a failure rate of more than 1% per year and include:
 - progestogen-only hormonal contraception, where inhibition of ovulation is not the primary mode of action
 - male or female condom with or without spermicide
 - cap, diaphragm or sponge with spermicide

Periodic abstinence and withdrawal are not acceptable methods of contraception. Female partners of male subjects must be informed by their male partners about the need to use one highly effective methods of birth control combined with an acceptable method of birth control as defined above.

Female subjects of childbearing potential must perform a negative urine pregnancy test prior to the first instillation of PP-001. In cohorts 1-3, an additional urine pregnancy tests will be performed during the safety visit on Study Day 8 and Study Day 28. In cohort 4, urine pregnancy tests will be performed at screening, on Study day 0 and on Study Day 20.

7. ADVERSE EVENTS

An AE is any untoward medical occurrence in a patient or clinical investigation subject administered a pharmaceutical product that does not necessarily have a causal relationship with this treatment. An AE can therefore be any unfavourable and unintended sign (including an abnormal laboratory finding), symptom, or disease temporally associated with the use of an IP, whether or not related to the IP.

Any pre-existing conditions or signs and/or symptoms present in a subject before the start of the study (i.e., before informed consent) should be recorded as medical/surgical history. Any medical occurrences that are new or worsened from the time of informed consent and up to and including the final visit must be reported as AEs or SAEs. All AEs and SAEs must be recorded irrespective of whether they are considered drug-related.

Subjects will be monitored throughout the study for adverse reactions to the study medications and/or procedures at each study visit. Questions will be posed in a non-leading manner so as not to bias the response. In addition to questioning at specific time points, subjects will be encouraged to report any AEs spontaneously. Subjects will also record any AEs occurring during the outpatient phase in a subject diary card. Any subject with an AE, SAE or clinically significant abnormal laboratory test value will be evaluated by the Investigator, or a monitoring physician, and will be treated and/or followed up until the symptoms or values have resolved or are assessed as stable by the Investigator. A physician, either at the Investigative site or at a nearby hospital emergency room, will administer treatment for any SAEs. Where appropriate, medical tests and examinations may be performed to ensure that an AE has fully resolved.

Adverse events and SAEs will be monitored throughout the study from the time a subject provides consent through to the final follow-up visit. Whenever possible, a specific disease or syndrome rather than individual associated signs and symptoms should be identified by the Investigator and

recorded on the subject's eCRF. However, if an observed or reported sign or symptom is not considered a component of a specific disease or syndrome by the Investigator, it should be recorded as a separate AE on the subject's eCRF.

Each AE or SAE reported will be assessed for severity and the date and time of onset (if available), relationship to dosing, duration and outcome of each event will be noted.

Laboratory abnormalities are not considered AEs unless they are associated with clinical signs and symptoms or require medical intervention.

The Investigator will exercise medical and scientific judgment in deciding whether an abnormal clinical laboratory finding or other abnormal assessment is clinically significant.

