4. STUDY POPULATION

4.1 Inclusion Criteria

Cohorts 1-3:

All subjects must meet all of the following criteria to be included in the study:

1. Male or female healthy volunteers 18–64 years of age.

2. Good general state of health (mentally and physically). Laboratory parameters and vital signs of subjects must be within the normal ranges (or judged as not clinically significant by the investigator) and subjects must not have a diagnosis of any eye or systemic disease that could affect the pharmacokinetics of PP-001.
3. Willing to provide a signed and dated written informed consent form.
4. Female subjects of childbearing potential must have a negative urine pregnancy test prior to the first administration on Day 0.
5. Male and female subjects must ensure that one highly effective method of contraception, combined with an acceptable method of contraception, is used for the entire duration of the study, from first dose up to the study follow-up visit. Subjects must agree to refrain from becoming pregnant or fathering a child in the 3 months following the last study drug administration. Male subjects must agree with their female partners, prior to screening, to use the above specified methods of contraception while receiving IP, and for 3 months after stopping IP.
6. Best-corrected visual acuity of 0.1 log minimal angle of resolution or better in both eyes (approximately 20/25 or better).
7. Intraocular pressure <21 mmHg with differences between eyes of <4 mmHg.

Cohort 4:

All subjects must meet all of the following criteria to be included in the study:

1. Male or female subjects 18–64 years of age with ocular surface inflammation in both eyes as defined below.
2. Ocular surface inflammation defined as an Ocular Surface Disease Index (OSDI) of 22 or more AND conjunctival hyperemia of Grade 2 on the Efron Scale or more in both eyes
3. Good general state of health (mentally and physically). Laboratory parameters and vital signs of subjects must be within the normal ranges (or judged as not clinically significant by the investigator) and subjects must not have a diagnosis of any eye disease except ocular surface inflammation.
4. Willing to provide a signed and dated written informed consent form.
5. Female subjects of childbearing potential must have a negative urine pregnancy test prior to the first administration

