5.1 Study Drug Treatment

5.1.1 Duration of Treatment

Subjects will receive up to four eye drops of PP-001 per day in a randomly assigned eye. Subjects will be treated initially for 1 day (Day 0) and then for 12 days (4 times daily, Days 8–19) in cohorts 1-3 and for 12 consecutive days (2 times daily, Days 0-11) in cohort 4.

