9.6 Safety Analysis

Safety will be evaluated in the Safety Analysis Set by presenting summaries of AEs and vital signs.

Summary tables will be provided for all treatment-emergent AEs (TEAEs). A TEAE is defined as an AE with a start date and time on or after the first dose of study drug. Adverse events will be coded using the Medical Dictionary for Regulatory Activities (MedDRA®). The number and percentage of subjects with TEAEs will be tabulated by system organ class and MedDRA Preferred Term for each treatment group and by severity and relationship to treatment.

Adverse events leading to premature discontinuation from the study drug and serious TEAEs will be presented either in a table or a listing.

Descriptive statistics of vital signs and the change from baseline for each scheduled evaluation will be summarised at each study visit and the worst overall post-baseline value will be provided. The number and percent of subjects with treatment-emergent values with potential clinical significance will be tabulated.

Descriptive statistics of laboratory parameters and the change from baseline for each scheduled evaluation will be summarised at each study visit. The number and percent of subjects with treatment-emergent values of potential clinical significance will be tabulated by parameter.

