1.3 Endpoints

1.3.1 Primary Endpoints

The primary endpoint will be safety and tolerability as assessed through:

- Adverse events
- Serious AEs (SAEs)
- Laboratory safety tests
- Vital signs
- Physical examination

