6. SAFETY ANALYSIS

6.1 Adverse Events

The following information will be analyzed descriptively and corresponding details on the subject level will be provided in data listings:

- Adverse Event (AE)
- AEs leading to premature discontinuation from the study drug
- Serious AEs
- AEs by severity
- AEs by causality
- AEs by SOC and PT

Definitions:

- In tables showing subjects with AEs by maximum severity, subjects will be counted only in the highest grading category, but events will be counted in each reported grading category.
- In tables showing AEs by maximum causality, subjects will be counted only in the strongest relationship category, but events will be counted in each category.

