7.1 List of Tables

No.	Legend	Comment
Overall study information		
1.1.1	Subject overview (all subjects)	
1.1.2	Protocol deviations (safety analysis set)	
1.1.3	Attended visits with dates (safety analysis set)	
1.1.4	Study completion (safety analysis set)	
1.1.5	Study drug administration (safety analysis set)	
1.2.2 -	Repeat tables for ITT analysis set, if not the same as safety analysis set.	
1.2.5		
Baseline evaluation		
2.1.1	Summary table of demographic information (safety analysis set)	
2.1.2	Summary table for medical and ophthalmic histories and prior and concomitant medication (safety analysis set)	
2.1.3	Non-pharmacologic treatments and procedures (safety analysis set)	
2.2.1 -	Repeat tables for ITT analysis set, if not the same as safety analysis set.	
2.2.3		
Pharmacodynamics Analysis		
3.1.1	Pharmacodynamics by time point (ITT analysis set)	
3.2.1	Repeat table for PP analysis set.	
Safety Analysis		
4.1	Summary table for adverse events (safety analysis set)	Including tests described in section 2.5.
4.2	Adverse events by SOC and PT (safety analysis set)	
4.3	Adverse events by severity (safety analysis set)	
4.4	Adverse events by maximum severity (safety analysis set)	"By maximum severity" is explained in section 6.1.
4.5	Adverse events by causality (safety analysis set)	
4.6	Adverse events by maximum causality (safety analysis set)	"By maximum causality" is explained in section 6.1.
4.7	Laboratory results by time point (safety analysis set)	

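### Neither the protocol nor the SAP requires the affected eye to be recorded for an adverse event or used in any AE table or test, although only one eye is dosed

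*Protocol*

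**What the plan says.** **Dosing.** Protocol 5.1.1: "Subjects will receive up to four eye drops of PP-001 per day in a randomly assigned eye". The other eye gets no study drug. In Cohort 4 that eye is diseased too, because protocol 4.1 admits "Male or female subjects 18–64 years of age with ocular surface inflammation in both eyes as defined below". Sections 5.2 and 6.4.2 supply a topical lubricant "as standard of care treatment for the control eye as needed", with each instillation entered in the diary.

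**Endpoint.** SAP 1.3.1: "The primary endpoint will be safety and tolerability as assessed through" five components, of which adverse events are the first.

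**Recording.** Protocol section 7: "Each AE or SAE reported will be assessed for severity and the date and time of onset (if available), relationship to dosing, duration and outcome". Nothing elsewhere in either document asks for the eye.

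**Tabulation.** Protocol 9.6: "The number and percentage of subjects with TEAEs will be tabulated by system organ class and MedDRA Preferred Term for each treatment group", and also by severity and relationship. SAP 6.1 has the same breakdowns, including "AEs by SOC and PT". In SAP 7.1 these become Tables 4.1 to 4.6: summary, SOC/PT, severity, maximum severity, causality and maximum causality. None is split by eye.

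**Testing.** SAP 2.5 attaches Fisher's exact tests to the AE summary table (Table 4.1) and states that the p-values are exploratory and the study is not powered for them.

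**The concern.** The trial asks whether the drop is safe for, and tolerated by, the eye that receives it. Stinging in the dosed eye bears on that question directly. An itch in the undosed eye, a reaction to the lubricant in the Cohort 4 control eye, or a headache bears on it much less. In the one AE summary that is tested, a subject with any of these counts the same.

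Events that occur at similar rates in both arms raise both incidences and compress the difference between PP-001 and placebo. In this trial the loss is avoidable. The dosed eye is chosen at random, so the fellow eye offers a within-subject comparison. The protocol already uses that idea for the ophthalmic examinations (6.3), which are done on both eyes to give an untreated comparison, but does not carry it over to adverse events.

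**Working it through.** The documents give no event rates, effect size, alpha or power, so there is no figure to reproduce. All rates below are assumptions, and a two-sided 5% level is assumed for illustration. Only the Cohort 4 allocation, 14 PP-001 to 7 placebo, comes from the documents (protocol section 3, SAP 1.2).

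**Model.** Let p be the risk of a treated-eye event, f of a fellow-eye event and n of a non-ocular event. Take f and n as equal in the two arms and all three as independent.

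- Ocular AE risk (all that SOC/PT can isolate) = 1 − (1 − p)(1 − f)
- Any-AE risk (Table 4.1) = 1 − (1 − p)(1 − f)(1 − n)

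The difference between arms is therefore (1 − b) times the treated-eye difference. For ocular events b = f. For any AE, 1 − b = (1 − f)(1 − n).

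**Treated eye 40% vs 10% (difference 30 points):**

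| What is counted | 1 − b | PP-001 | Placebo | Difference (points) | Fisher power, 14 vs 7 |
|---|---|---|---|---|---|
| Treated eye only | 1 | 40% | 10% | 30 | 15% |
| Ocular, f = 10% | 0.90 | 46% | 19% | 27 | 13% |
| Ocular, f = 25% | 0.75 | 55% | 32.5% | 22.5 | 9% |
| Any AE, f = 10%, n = 20% | 0.90 × 0.80 = 0.72 | 56.8% | 35.2% | 21.6 | 8% |
| Any AE, f = 25%, n = 30% | 0.75 × 0.70 = 0.525 | 68.5% | 52.75% | 15.75 | 6% |

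Example, last row: 1 − 0.6 × 0.525 = 0.685 and 1 − 0.9 × 0.525 = 0.5275.

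**Treated eye 60% vs 10% (difference 50 points).** The factors are the same. Among ocular events the difference is 45 points (f = 10%) or 37.5 points (f = 25%). For any AE it is 36 or 26.25 points. Power goes from 52% to 38% and 25% among ocular events, and to 23% and 15% for any AE.

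Power was found by enumerating all binomial outcomes for 14 and 7 subjects. It shows what dilution does to the planned test; it is not a target the trial set itself.

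**The same effect in counts.** With no placebo subject affected, 7 of 14 on PP-001 gives p = 0.047. If 2 of the 7 placebo subjects have any unrelated event, 12 of 14 are needed to reach p below 0.05.

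**What is due to the missing eye.** The ocular rows isolate it: 30 points become 27 or 22.5. The further fall in the any-AE rows comes from non-ocular events, which Table 4.2 already separates, though without a test. The f = 25% rows are an upper illustration, since they set placebo fellow-eye risk (25%) above placebo treated-eye risk (10%) and nothing in the documents supports that. With equal placebo risks of 10%, the missing eye alone costs 3 of 30 points, or 5 of 50.

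**The case against.** **The eye may in fact be captured.** A reader might infer that adverse events are recorded without the eye. The documents do not establish that. The list in protocol section 7 is silent rather than exclusive: it does not name seriousness, yet SAP Listing 4.2 expects a seriousness assessment. The eCRF is not among the documents, and the eye could sit in a field or in the verbatim term. This stands. What can be said is that neither document requires the eye, and that no table or test uses it.

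**The AE output is not one undifferentiated count.** A reader might also infer that non-ocular events weigh the same as ocular ones in every AE table. That is not so. Table 4.2 puts a headache in a different class from an eye event. Tables 4.5 and 4.6 split by causality, which protocol 7.2 tells the investigator to judge in the light of concomitant therapy, and lubricant use is logged. This stands for those tables. But causality is a judgement and not a location, no table separates the two eyes, and the tests sit only on Table 4.1.

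**The tests are exploratory and tiny.** This stands. No confirmatory conclusion is at risk, and in the 40% vs 10% example power is too low to be useful with or without the change. Escalation rests on the data safety monitoring board, which sees ophthalmic examinations as well as AEs (protocol 10.2). The point is mainly about description.

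**Local tolerability is measured in other ways.** This stands in part. Both eyes are examined, but these are pharmacodynamic endpoints and SAP section 5 does not state a treated-versus-fellow split. The ocular discomfort score (protocol 6.1.7) is a global score with no eye specified. Nor is the Cohort 4 fellow eye a clean control, since it may receive lubricant.

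**Conclusion.** The point holds as an omission in the plan. In a trial that doses one randomly assigned eye, neither document requires the affected eye to be recorded for an adverse event or used in any AE table or test. Treated-eye and fellow-eye events cannot be told apart in any planned AE table, and the tested summary adds non-ocular events to both.

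The shrinkage factor (1 − b) follows from the model; its size depends on assumed rates. For a 30-point treated-eye difference it gives 27 to 22.5 points among ocular events, and 21.6 to 15.75 points in the any-AE row. The lower fellow-eye background is the better supported end, so the loss due to the eye alone is modest. The calculation assumes independent events and equal background in the two arms. Correlation between the eyes, which is plausible in bilateral disease, could move the figures either way.

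The consequence falls on the descriptive safety tables and on exploratory p-values. It does not invalidate the safety assessment. It is worth changing because the change is cheap and is best made before unblinding.

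**What to change.** 1. **Data.** Make sure each adverse event carries one code: study eye, fellow eye, both eyes, or non-ocular. If the eCRF already holds this, nothing needs adding; if not, add one field and name the item in protocol section 7.
2. **Cohorts 1–3.** Back-fill the code from source documents or verbatim terms, allowing unknown. Do this before database closure, because SAP 2.1 and 2.3 place unblinding after it and assigning the eye with treatment known would invite bias.
3. **Tables.** In SAP 6.1 and Tables 4.1 to 4.6, show study-eye events (including both eyes), fellow-eye events and non-ocular events as separate rows beside the total.
4. **Tests.** Run the two existing PP-001 versus placebo comparisons in SAP 2.5 (Cohorts 1–3 pooled, and Cohort 4) on study-eye events as well as on any event, still labelled exploratory.

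**Cost.** At most one eCRF field, a blinded back-fill and extra table rows, with no added subjects, visits or procedures. Two downsides remain: the eye may be unrecoverable for a few 2018–2019 events, and there will be a few more exploratory p-values.
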